### **2.2 Analysis sets**

For all analysis sets, patients will be analyzed according to the study treatment received unless indicated otherwise.

The safety analysis set will include all patients who received any study drug.

The PK analysis set will include all patients with at least one available valid (i.e. not flagged for exclusion) PK concentration measurement, who received any study drug and with no protocol deviations that impact PK data.

The PD analysis set will include all patients with available PD data and no protocol deviations with relevant impact on PD data, with data exclusion including but not limited to:

Commercially Confidential Information

2. EOS visit assessments when they were done earlier than day 135.
3. EOS visit assessments when they were done > 10 days from the last dose.

Commercially Confidential Information

Protocol deviation impact, including the impact due to COVID-19, will be documented appropriately and assessed by the Sponsor study team, including the Medical and Study Leads with input from the trial team.

### **2.3 Patient disposition, demographics and other baseline characteristics**

Demographic and other baseline data including disease characteristics will be listed and summarized descriptively by treatment group for the Safety set and PD analysis set.

Categorical data will be presented as frequencies and percentages. For continuous data, mean, standard deviation, median, minimum, and maximum will be presented. For selected parameters, 25th and 75th percentiles may also be presented.

Relevant medical histories and current medical conditions at baseline will be listed by treatment group, system organ class and preferred term.

### **2.4 Treatments (study treatment, rescue medication, concomitant therapies, compliance)**

Concomitant medications and significant non-drug therapies prior to and after the start of the study treatment will be listed by treatment group according to the WHO Drug Reference List, which employs the Anatomical Therapeutic Chemical classification system.

### **2.5 Analysis of the primary objective**

The primary objective of this study is to assess the safety and tolerability of LMB763 as well as the efficacy of LMB763 on albuminuria in patients with diabetic nephropathy during 24 weeks of treatment.

#### **2.5.1 Primary endpoint**

For analytical purposes, all safety data, including laboratory measurements, vital signs, adverse events, ECG, are considered primary endpoints.

For efficacy evaluation, log-transformed ratios to baseline UACR and 24-hour urine albumin excretion at Week 24 are the primary endpoints.

The raw value, ratio to baseline and log-transformed ratio to baseline of UACR will be plotted for each subject over time.

## 2.5.2 Statistical hypothesis, model, and method of analysis

### 2.5.2.1 Safety endpoints

For all safety analyses, the safety set will be used. Safety and tolerability data will be summarized. Formal statistical analysis will not be performed on the safety and tolerability data.

#### Adverse events

All information obtained on AEs will be displayed by treatment group and patient.

The number (and percentage) of patients with treatment emergent adverse events (events started after the first dose of study medication or events present prior to start of treatment but increased in severity based on preferred term) will be summarized in the following ways:

- by treatment, primary system organ class and preferred term.
- by treatment, primary system organ class, preferred term and maximum CTCAE grade

Separate summaries will be provided for study medication related AEs, death, SAEs, other significant AEs, AEs leading to study discontinuation of study treatment, study-drug related AEs leading to study discontinuation of study treatment, AEs leading to dose interruption/reduction and COVID-19 events.

A patient with multiple AEs within a primary system organ class is only counted once towards the total of the primary system organ class.

For the legal requirements of ClinicalTrials.gov and EudraCT, two required tables on treatment emergent adverse events which are not serious adverse events with an incidence greater than 0% and on treatment emergent serious adverse events and SAE suspected to be related to study treatment will be provided by system organ class and preferred term on the safety set population.

If for a same patient, several consecutive AEs (irrespective of study treatment causality, seriousness and severity) occurred with the same SOC and PT:

- a single occurrence will be counted if there is  $\leq 1$  day gap between the end date of the preceding AE and the start date of the consecutive AE
- more than one occurrence will be counted if there is  $> 1$  day gap between the end date of the preceding AE and the start date of the consecutive AE

For occurrence, the presence of at least one SAE / SAE suspected to be related to study treatment / non SAE has to be checked in a block e.g., among AE's in a  $\leq 1$  day gap block, if at least one SAE is occurring, then one occurrence is calculated for that SAE.

The number of deaths resulting from SAEs suspected to be related to study treatment and SAEs irrespective of study treatment relationship will be provided by SOC and PT.

In addition, the following figures will be plotted.

1. The pruritus events over time by toxicity grade will be plotted by subject.
2. The dosing records over time will be plotted by subject for those with pruritus events.
3. The pruritus events and dosing records over time will also be plotted in the same figure by subject for those with pruritus events.

## **Vital signs**

All vital signs data will be listed by treatment group, patient, and visit/time and if ranges are available, abnormalities (and relevant orthostatic changes) will be flagged. Summary statistics will be provided by treatment and visit/time.

## **12-lead ECG**

All ECG data will be listed by treatment group, patient and visit/time, abnormalities will be flagged. Summary statistics will be provided by treatment and visit/time.

## **Clinical laboratory evaluations**

All laboratory data will be listed by treatment group, patient, and visit/time and abnormalities will be flagged. Summary statistics will be provided by treatment and visit/time.

### **2.5.2.2 Efficacy and/or pharmacodynamic endpoints**

For all efficacy PD analyses, the PD set will be used.

A Mixed Model for Repeated Measures (MMRM) analysis will be performed for log-transformed ratio to baseline UACR measured at each visit. The model will include effects for log-transformed baseline, treatment, visit, treatment by visit interaction and visit by log-transformed baseline interaction. An unstructured variance-covariance matrix will be used to account for correlation among multiple measurements from the same patient and variance heterogeneity.

Similarly an Analysis of Covariance (ANCOVA) with treatment as the classification factor and log-transformed baseline as the covariate will be conducted for log-transformed ratio to baseline 24-hour urine albumin excretion.

Point estimates, the associated confidence intervals as well as the p-values for treatment difference at each visit will be provided within the MMRM/ANCOVA framework. The null hypothesis of no treatment difference in UACR or 24-hour urine albumin excretion will be tested at the one-sided 0.1 significance level. A treatment difference of at least 25% in favor of LMB763 will be considered clinically significant.

### **2.5.3 Handling of missing values/multiple values/censoring/discontinuations.**

Missing data will not be imputed.

Assuming data is missing at random, a patient with a missing value at a visit will still contribute to the estimation of the treatment effect at that particular visit as the likelihood-based MMRM borrows information from non-missing values of this patient and other patients.

For central lab data collected at scheduled visits, the following sequential approach will be taken before data summary and analysis.

1. Take the average by subject, date and time for each parameter first.
- 2a. Derive baseline as the last available value prior to Day 1 dosing for each subject and parameter.
- 2b. Take the average by subject and visit for each parameter and then merge with the dataset containing baseline from 2a by subject and parameter.

The same approach as described above will be taken for vital sign and VAS data.

Local lab data will be included along with central lab data in the data listings and liver/renal event tables.

For ECG, 3 measurements on each visit are expected. The mean value will be used in the analyses even though the times are different.

For the analyses of liver abnormality and renal events, the most extreme value expressed as the multiple of the upper limit of normal (xULN) in a visit will be used for analyses.

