## 5.2 Exclusion criteria

Patients meeting any of the following criteria are not eligible for inclusion in this study.

Commercially Confidential Information

3. History of Type 1 diabetes mellitus
4. Uncontrolled type 2 diabetes mellitus as evidenced by HbA1c  $>11\%$  at screening
5. The presence of kidney disease, other than diabetic nephropathy, at screening including:
  - Primary kidney disease, including, but not limited to primary glomerulonephritis, focal segmental glomerulosclerosis, polycystic kidney disease, or membranous nephropathy;
  - Secondary kidney disease, other than diabetic nephropathy, including but not limited to lupus nephritis, obstructive uropathy, and renovascular disease;
  - History of acute renal dialysis or acute kidney injury stage 2 or 3 as defined in the Kidney Disease: Improving Global Outcomes [KDIGO] guidelines ([Okusa and Davenport 2014](#))

6. Severe renal impairment manifesting as serum creatinine-based eGFR <30 mL/min/1.73 m^2 at screening, as determined by the CKD-EPI formula (Levey and Stevens 2010)
7. History of renal transplant or planned renal transplant during the study
8. Diagnostic or interventional procedure requiring any potentially nephrotoxic contrast agent within 4 weeks of the first screening visit, or planned during the study
9. Uncontrolled hypertension (Whelton et al 2018), despite receiving anti-hypertensive therapy, as evidenced by BP >150/90 mm Hg at rest at screening as determined by the lowest of 3 measurements obtained over approximately 15 minutes while sitting
10. History or presence of liver disease at screening including:
  - Active Hepatitis B or C virus (HCV, HBV) infection
    - *Note: A positive HBV surface antigen (HBsAg) test excludes a patient*
  - Primary biliary cholangitis (PBC)
  - Primary sclerosing cholangitis (PSC)
  - Alcoholic liver disease
  - Cirrhosis
  - Definite autoimmune liver disease or overlap hepatitis
  - Suspected or confirmed Gilbert's syndrome
  - Known bile duct obstruction
  - Liver transplantation or current placement on a liver transplant list
  - Suspected or proven liver cancer
    - *Note: Patients with NASH or NAFLD are not excluded, if their transaminase levels comply with exclusion criterion 11*
11. Serum ALT or AST >1.5 x ULN at screening.
12. Clinical evidence of hepatic decompensation or severe liver impairment as defined by the presence of any of the following abnormalities at screening:
  - Serum albumin <LLN

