## 16.2 Appendix 2: Liver event and Laboratory trigger Definitions and Follow-up Requirements

**Table 16-1 Liver Event and Laboratory Trigger Definitions**

	Definition/ threshold
LIVER LABORATORY TRIGGERS	

• <math>3 \times \text{ULN} < \text{ALT} / \text{AST} \leq 5 \times \text{ULN}</math>

• <math>1.5 \times \text{ULN} < \text{TBL} \leq 2 \text{ULN}</math>

LIVER EVENTS	

• <math>\text{ALT or AST} > 5 \times \text{ULN}</math>

• <math>\text{ALP} > 2 \times \text{ULN}</math> (in the absence of known bone pathology)

• <math>\text{TBL} > 2 \times \text{ULN}</math> (in the absence of known Gilbert syndrome)

• Potential Hy's Law cases (defined as <math>\text{ALT or AST} > 3 \times \text{ULN}</math> and <math>\text{TBL} > 2 \times \text{ULN}</math> [mainly conjugated fraction] without notable increase in ALP to <math>> 2 \times \text{ULN}</math>)

• Any clinical event of jaundice (or equivalent term)

• <math>\text{ALT or AST} > 3 \times \text{ULN}</math> accompanied by (general) malaise, fatigue, abdominal pain, nausea, or vomiting, or rash with eosinophilia

• Any adverse event potentially indicative of a liver toxicity*

\*These events cover the following: hepatic failure, fibrosis and cirrhosis, and other liver damage-related conditions; the non-infectious hepatitis; the benign, malignant and unspecified liver neoplasms TBL: total bilirubin; ULN: upper limit of normal

[Chalasani and Regev 2016](#)

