**Table 16-2 Follow Up Requirements for Liver Events and Laboratory Triggers**

Criteria	Actions required	Follow-up monitoring
Potential Hy's Law case a	
 
Discontinue the study treatment immediately
 
Hospitalize, if clinically appropriate
 
Establish causality
 
Complete liver CRF
 
	ALT, AST, TBL, Alb, PT/INR, ALP and $\gamma$ -GT until resolution c (frequency at investigator discretion)
ALT or AST		
for patients with normal baseline: $> 8 \times$ ULN For patients with elevated baseline $> 8 \times$ ULN or $> 500$ U/L whichever comes first	
 
Discontinue the study treatment immediately
 
Hospitalize if clinically appropriate
 
Establish causality
 
Complete liver CRF
 
	ALT, AST, TBL, Alb, PT/INR, ALP and $\gamma$ GT until resolution c (frequency at investigator discretion)
For patients with normal baseline: $> 5$ to $\leq 8 \times$ ULN For patients with elevated baseline: $>5$ to $\leq 8 \times$ ULN or $>5X$ ULN to $\leq 500$ U/L whichever comes first	
 
Repeat LFT within 48 hours
 
If elevation persists, continue follow-up monitoring
 
If elevation persists for more than 2 weeks, discontinue the study drug
 
Establish causality
 
Complete liver CRF
 
	ALT, AST, TBL, Alb, PT/INR, ALP and $\gamma$ GT until resolution c (frequency at investigator discretion)
$> 3 \times$ ULN accompanied by symptoms b	
 
Discontinue the study treatment immediately
 
Hospitalize if clinically appropriate
 
Establish causality
 
Complete liver CRF
 
	ALT, AST, TBL, Alb, PT/INR, ALP and $\gamma$ GT until resolution c (frequency at investigator discretion)
$> 3$ to $\leq 5 \times$ ULN (patient is asymptomatic)	
 
Repeat LFT within the next week
 
If elevation is confirmed, initiate close observation of the patient
 
	Investigator discretion Monitor LFT within 1 to 4 weeks
ALP (isolated)		

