$> 2 \times$ ULN (in the absence of known bone pathology)	
 
Repeat LFT within 48 hours
 
If elevation persists, establish causality
 
Complete liver CRF
 
	Investigator discretion Monitor LFT within 1 to 4 weeks or at next visit
TBL (isolated)		

Criteria	Actions required	Follow-up monitoring
> 2 × ULN (in the absence of known Gilbert syndrome)	
 
Repeat LFT within 48 hours
 
If elevation persists, discontinue the study drug immediately
 
Hospitalize if clinically appropriate
 
Establish causality
 
Complete liver CRF
 
	ALT, AST, TBL, Alb, PT/INR, ALP and γGT until resolution c (frequency at investigator discretion) Test for hemolysis (e.g., reticulocytes, haptoglobin, unconjugated [indirect] bilirubin)
> 1.5 to ≤ 2 × ULN (patient is asymptomatic)	
 
Repeat LFT within the next week
 
If elevation is confirmed, initiate close observation of the patient
 
	Investigator discretion Monitor LFT within 1 to 4 weeks or at next visit
Jaundice	
 
Discontinue the study treatment immediately
 
Hospitalize the patient
 
Establish causality
 
Complete liver CRF
 
	ALT, AST, TBL, Alb, PT/INR, ALP and γGT until resolution c (frequency at investigator discretion)
Any AE potentially indicative of a liver toxicity*	
 
Consider study treatment interruption or discontinuation
 
Hospitalization if clinically appropriate
 
Establish causality
 
Complete liver CRF
 
	Investigator discretion

aElevated ALT/AST > 3 × ULN and TBL > 2 × ULN but without notable increase in ALP to > 2 × ULN

b(General) malaise, fatigue, abdominal pain, nausea, or vomiting, or rash with eosinophilia

cResolution is defined as an outcome of one of the following: (1) return to baseline values, (2) stable values at three subsequent monitoring visits at least 2 weeks apart, (3) remain at elevated level after a maximum of 6 months, (4) liver transplantation, and (5) death.

[Chalasani and Regev 2016](#)

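### Using the highest ALP in a visit can remove a patient from the potential Hy's Law category, because that definition requires ALP not above 2 x ULN

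*SAP*

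**What the plan says.** **Within-visit rule.** SAP section 2.5.3 says that for liver abnormality and renal event analyses "the most extreme value expressed as the multiple of the upper limit of normal (xULN) in a visit will be used for analyses". It makes no exception for any liver parameter. The same section adds: "Local lab data will be included along with central lab data in the data listings and liver/renal event tables".

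**Definition.** Footnote a of Protocol Table 16-2 defines a potential Hy's Law case as "Elevated ALT/AST > 3 × ULN and TBL > 2 × ULN but without notable increase in ALP to > 2 × ULN". Table 16-1 carries the same ALP condition ("mainly conjugated fraction] without notable increase in ALP to" > 2 x ULN). Neither table says that all the tests must come from one sample.

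**Other liver events.** Table 16-1 also lists two single-parameter events: ALP > 2 x ULN ("in the absence of known bone pathology") and TBL > 2 x ULN. The TBL row of Table 16-2 reads "> 2 × ULN (in the absence of known Gilbert syndrome" and closes the bracket there. Protocol section 5.2 excludes at entry "Suspected or confirmed Gilbert's syndrome".

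**Repeat samples.** Protocol section 10.2.1 asks for repeat liver chemistry, ALP included, to confirm an elevation, and allows a local laboratory when central results would be slow. In Table 16-2 the instruction "Repeat LFT within 48 hours" belongs to the rows for ALT/AST above 5 and up to 8 x ULN, isolated ALP and isolated TBL. The potential Hy's Law row leaves the monitoring frequency to the investigator.

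The readable SAP text does not mention Hy's Law and does not say to which visit a repeat sample belongs.

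**The concern.** A most-extreme-value rule is usually chosen because it errs towards finding events. That works when the criterion is a lower bound, as for ALT, AST and TBL. Potential Hy's Law also has an upper bound, on ALP. For that one component the highest value makes the criterion harder to meet.

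The patients concerned are likely to be re-sampled, since the protocol asks for confirmation and follow-up of liver events. Each further ALP filed under the visit is another chance to exceed 2 x ULN and remove the label.

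At stake is a category count. The SAP treats safety data as primary endpoints and summarises them without formal testing, so the counts are the result. With about 116 patients, one potential Hy's Law case against none would change how the liver findings read. Separate TBL and ALP entries do not convey the same finding, and Table 16-2 gives potential Hy's Law a row of its own.

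**Working it through.** The plan states no figure on this point, so there is nothing to reproduce. The check has three steps.

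**1. Worked example (values chosen for illustration, in x ULN)**

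| | ALT | TBL | ALP | Potential Hy's Law? |
|---|---|---|---|---|
| First sample | 4.0 | 2.5 | 1.8 | Yes: 4.0 > 3, 2.5 > 2, 1.8 not > 2 |
| Repeat, same visit | 3.8 | 2.6 | 2.1 | No: 2.1 > 2 |
| Visit maxima | 4.0 | 2.6 | 2.1 | No: 2.1 > 2 |

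The first sample qualifies but the visit does not. On the visit maxima the patient still meets TBL > 2 x ULN (2.6) and ALP > 2 x ULN (2.1), both liver events in Table 16-1.

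**2. Enumeration of two samples per visit**

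Grid: ALT 1, 2.5, 3.5, 6, 9; TBL 0.8, 1.8, 2.2, 3; ALP 1, 1.9, 2.1, 3. This gives 5 x 4 x 4 = 80 possible samples and 80 x 80 = 6400 pairs.

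- Pairs with at least one sample meeting the definition: 1776.
- Of these, pairs that lose the label on visit maxima: 960.
- Of the 960, pairs that fall under no liver event: 0.
- Pairs where no single sample qualifies but the maxima do, because ALT/AST and TBL come from different samples: 192.

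These counts depend on the grid and are not rates. They show that both errors are possible and that the loss is confined to the Hy's Law category.

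**3. Chance of losing the label (all inputs assumed)**

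Assume ALP is log-normal around an underlying level m (x ULN) with sample-to-sample coefficient of variation CV, samples are independent, and repeats are filed under the same visit. Assume also that the first sample qualifies, so its ALP is at most 2 x ULN.

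- sigma = sqrt(ln(1 + CV^2))
- q = P(one repeat ALP > 2) = 1 - Phi(ln(2/m) / sigma)
- Loss with one repeat = q; with two repeats = 1 - (1 - q)^2

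For m = 1.8 and CV 10%: sigma = 0.0998; ln(2/1.8) = 0.1054; ratio 1.056; q = 0.145; with two repeats 1 - 0.855^2 = 0.27.

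| Underlying ALP | Repeats | CV 6% | CV 10% | CV 15% |
|---|---|---|---|---|
| 1.5 x ULN | 1 | 0.0% | 0.2% | 2.7% |
| 1.5 x ULN | 2 | 0.0% | 0.4% | 5.3% |
| 1.8 x ULN | 1 | 3.9% | 14.5% | 24.0% |
| 1.8 x ULN | 2 | 7.7% | 27.0% | 42.2% |
| 1.9 x ULN | 1 | 19.6% | 30.4% | 36.6% |
| 1.9 x ULN | 2 | 35.4% | 51.5% | 59.7% |

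These are conditional on a qualifying first sample. Without that condition, the probability that the first ALP is at most 2 and the repeat is above 2 is q(1 - q). For m = 1.8 and CV 10% that is 0.145 x 0.855 = 12.4%.

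**The case against.** **The patient is still in the table.** A reader might infer that a true case disappears from the liver event table. The documents do not support that. Every potential Hy's Law case has TBL > 2 x ULN, which is a liver event by itself, and the Gilbert exception should not apply to eligible patients. The ALP that removes the label is normally a second liver event. This objection stands in full: only the Hy's Law category loses the case.

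**The net direction is not fixed.** A reader might also call the rule anti-conservative for Hy's Law overall. It is so for ALP. But taking the highest ALT/AST and TBL from different samples can create cases, as the 192 pairs show. The definition does not demand one sample, so those are not plainly false, and it is likewise open whether a patient whose repeat ALP exceeds 2 x ULN is a true case.

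**The mechanism is partly inferred.** The SAP does not say that the combined criterion is built from visit maxima, and repeats might be filed as unscheduled visits. Both points are fair. However, this is the only rule stated for liver analyses, it has no ALP exception, and local values are explicitly included. A programmer following it as written would get the result in the example.

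**Safeguards exist.** Discontinuation and follow-up rest on the investigator's reading of results, not on this summary rule. All laboratory values are listed by patient and visit/time with abnormalities flagged, so the qualifying sample can still be seen. This limits the consequence to the summary, where a reader would have to find the case unaided.

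**Conclusion.** The point holds for the potential Hy's Law category only. Applied as written, the visit rule can take the label from a sample that met the protocol's definition. The count of patients with any liver event does not change, and patient management does not depend on the rule.

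The size is conditional. The loss requires at least two ALP values in one visit, on either side of 2 x ULN. With one repeat it is about 4% to 24% of qualifying cases at an underlying ALP of 1.8 x ULN and at most 3% at 1.5 x ULN. The ALP levels, the CVs, the number of repeats and their filing under the same visit are all assumptions, so no rate for this trial follows. Few cases are to be expected in about 116 patients, but each one matters to the liver conclusion and the remedy is cheap, so the change should be made.

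**What to change.** In SAP section 2.5.3:

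- Keep the most-extreme-value rule for single-parameter thresholds.
- For potential Hy's Law, do not use the visit-maximum ALP. Take ALP from the same sample date as the qualifying ALT/AST and TBL elevation, and count the patient if any post-baseline date meets the protocol definition, whatever the ALP on other dates.
- Show cases that arise only by combining ALT/AST and TBL from different dates within a visit separately, as non-concurrent. A strict same-date requirement on those two tests would otherwise drop patients whom the visit maxima capture, and the definition does not require one sample.
- State how repeat and local samples are assigned to visits.

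The cost is a few lines in the SAP and a by-date derivation in the liver event program. No new data are needed, and the protocol's definition and clinical actions stay as they are.
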